## 6. Study Procedures and Timelines

### 6.1 Study and Timeline Overview

Patients will be identified by the medical and research staff at the LAM clinic at the University of Cincinnati Medical Center. Study staff will screen up to 60 patients over 15 months with a goal of enrolling 25 participants. Patients who meet eligibility criteria, provide informed consent and are enrolled in the study will receive instructions regarding resveratrol dosage, route and administration. An 8-week supply of resveratrol will be provided at visit 1. Patients will begin resveratrol at a starting dose of 250mg daily, and increase the dose in two increments to a maximum dose of 1000mg daily. If patients do not tolerate a certain dose of resveratrol, the dose will be reduced to the last tolerated strength. Patients will remain on the last well-tolerated dose of resveratrol for the entire study duration. Patients who are unable to tolerate the lowest dose of resveratrol will be withdrawn from study.

The patients will be given a copy of the informed consent form. Patients will be given ample time to read and discuss the consent form with the study staff. The study staff will then answer any remaining questions asked by the patients. The patients will be offered the option of signing the consent form. Those who agree to participate will undergo the remainder of screening visit.

Prior to starting study drug, pre/post bronchodilator spirometry, diffusion capacity of carbon monoxide (DLCO), and serum VEGF-D will be obtained to establish baseline values prior to study drug initiation. The best values for FEV1 and FVC obtained during the spirometry maneuvers will be used. Patients will be followed with serial spirometry and VEGF-D levels collected at the initial visit, followed by week 8, week 16 and week 24 visits. DLCO will also be obtained at the 24-week visit in addition to spirometry.

For patients who agree to the home spirometry study, we will teach them on the proper technique to perform, record and transmit home spirometry, and provide them with a home spirometer. The patients will perform their first test during the initial visit and we will use those values to compare the home spirometer values with the office-based spirometry values. After that patients will be instructed to perform home spirometry once a week as detailed in Section 5.7.

Section 6.2 provides a summary of the study timeline and procedures.

## 6.2 Schedule of Events:

Event	Screening Visit*	Initial Visit	Week 2	Week 4	Week 8	Week 12	Week 16	Week 18	Week 20	Week 24
Visit number	0 or Phone	1	Lab check	Phone	2	Phone	3	Lab check	Phone	4
Informed consent	X									
History and physical		X			X		X			X
CBC, CMP		X			X		X			X
Lipid panel		X			X					X
Serum VEGF-D	X	X			X		X			X
Sirolimus level		X	X***	X***	X	X***	X	X***	X***	X
Urine Pregnancy Test**		X			X		X			
Saved serum and plasma		X			X		X			X
Spirometry post BD		X			X		X			X
Diffusion capacity		X								X
Home spirometry dispensed		X****								
Review concomitant meds		X		X	X	X	X		X	X
Review adverse events				X	X	X	X		X	X
SGRQ		X			X		X			X
ATAQ-LAM		X			X		X			X
EuroQOL		X			X		X			X
SD-SOB		X			X		X			X

Window for all visits after the initial visit:  $\pm 7$  days, except Weeks 2 and 18 where the window is  $\pm 3$  days

\* Screening visit can be the initial visit if a patient meets all inclusion/exclusion criteria. Informed consent for study inclusion can be obtained remotely over the phone rather than in-person. VEGF-D levels to confirm eligibility for trial participation can be drawn remotely rather than an in-person visit.

\*\* Only required for women of childbearing potential.

\*\*\* Can be drawn remotely. This is a trough level to be obtained  $24 \pm 4$  hours after the last sirolimus dose.

\*\*\*\* FEV1 and FVC will be obtained once weekly from patients agreeing to participate in the home spirometry sub study. Detailed instructions regarding the proper use of the home spirometer will be provided at the time of enrollment, along with access to detailed instruction manuals for future use. Once a week, patients will perform at least three spirometric measurements at approximately the same time, and record the best FEV1 and FVC values as their weekly results. These results, along with the associated flow-volume and volume-time loops will then be transmitted electronically to the study coordinator.

ATAQ-LAM: A Tool to Assess Quality of Life in LAM, BD: Bronchodilators, CBC: complete blood count, CMP: comprehensive metabolic panel, SGRQ: St. George's Respiratory Questionnaire, SD-SOB: San Diego Shortness of Breath scale, VEGF-D: Vascular Endothelial Growth Factor-D.

## 6.3 Study Visits

### Screening/Initial Visit

At the screening visit, the consent form will be presented to the potential patient. If the patient is competent to understand the risks, agrees to participate and provides informed consent and HIPAA release, the patient will undergo screening. Patients will also be informed about the home spirometry portion of this study, and given the option to opt-in or opt-out of the home spirometry evaluation. Patients may enroll in the clinical trial without agreeing to participate in the home spirometry portion. During this visit, we will review the inclusion/exclusion criteria, obtain a urine pregnancy test for women of childbearing potential (defined as any fertility status other than natural or surgical menopause or post hysterectomy), and check a serum VEGF-D level (if two previous stable values post initiation of sirolimus are not drawn). The screening visit and VEGF-D testing can be accomplished either remotely or in-person. If patients meet the study inclusion criteria, the screening visit can be their initial study visit. We anticipate that in most patients the screening visit will be the initial study visit, and the following additional steps will be completed during the visit:

- Review current medications.
- Review medical history and conduct a physical examination.
- Perform spirometry with appropriate safety precautions. All spirometry tests during all visits will be performed after supervised administration of bronchodilator in the pulmonary function laboratory.
- Perform diffusion capacity (DLCO) testing. DLCO will be performed in a supervised setting in the pulmonary function laboratory.
- Obtain clinical labs including: complete blood count (CBC), comprehensive metabolic panel (CMP), lipid panel, serum VEGF-D, sirolimus level, urine pregnancy test, and urinalysis.
- Quality of life, dyspnea and fatigue assessments
- Dispense resveratrol tablets for the next 8 week supply.

- Provide a drug diary to document drug compliance. Patients will bring the drug diary at each subsequent visit
- If the patient has consented obtain a blood sample to be stored on-site for potential future use
- If the patient has consented, instruct them on the proper technique to perform home spirometry, provide them with a home unit, and obtain the first set of FEV1 and FVC values. Patients will also be taught on how to record and transmit electronically the home spirometry values on a weekly basis throughout the 24-week trial duration.

### **Lab Check (Week 2 ± 3 days)**

During this study, the patient will have a sirolimus level checked for safety monitoring. This level can be drawn remotely.

### **Phone Visit (Week 4 ± 7 days)**

During this visit a study coordinator will contact the patient and review the interval history in detail. A report of any adverse events will be assembled in detail, along with a review of their concurrent medications. Any concerns brought up during this phone call will be reviewed with the investigator. In addition, sirolimus level for safety monitoring will be drawn at this visit. The sirolimus level can be drawn remotely.

### **Visit 2 (Week 8 ± 7 days)**

During this visit the following will be performed:

- Obtain a urine pregnancy test for women of childbearing potential
- Obtain urinalysis
- Review current medications
- Review the interval medical history, and perform a physical examination
- Perform spirometry after supervised administration of bronchodilator in the pulmonary function laboratory
- Quality of life, dyspnea and fatigue assessments
- Obtain blood for CBC, CMP, lipid panel, VEGF-D measurement and sirolimus level; if the patient has consented obtain an additional sample to be stored on-site for potential future use
- Dispense resveratrol tablets for the next 8 weeks
- Review drug diary and any reported adverse events
- Arrange for inter-visit phone call conduct

### **Phone Visit (Week 12 ± 7 days)**

During this visit a study coordinator will contact the patient and review the interval history in detail. A report of any adverse events will be assembled in detail, along with a review of their concurrent medications. Any concerns brought up during this phone call will be reviewed with the investigator. In addition, sirolimus level for safety monitoring will be drawn at this visit. The sirolimus level can be drawn remotely.

### **Visit 3 (Week 16 ± 7 days)**

During this visit, the following will be performed:

- Obtain a urine pregnancy test for women of childbearing potential
- Obtain urinalysis
- Review current medications
- Review the interval medical history, and perform a physical examination
- Perform spirometry after supervised administration of bronchodilator in the pulmonary function laboratory
- Quality of life, dyspnea and fatigue assessments
- Obtain blood for CBC, CMP, VEGF-D measurement and sirolimus level; if the patient has consented obtain an additional sample to be stored on-site for potential future use
- Dispense resveratrol tablets for the next 12 weeks
- Review drug diary and any reported adverse events

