
	
have anticancer, anti-inflammatory, and anti-oxidant properties. Resveratrol has a complex mechanism of mTOR regulation. In addition, resveratrol inhibits the activity of Akt, AMPK and S6K1. Recent pre-clinical studies performed on TSC2 null cells as well as murine models have demonstrated that a combination of resveratrol and sirolimus leads to downregulation of autophagy and promotes apoptosis in TSC2 null cells, decreases the metastatic capability of uterine leiomyoma-derived smooth muscle cells, and causes a significant reduction in the size and growth of TSC2 deficient xenograft tumors.
 
The unmet need for a remission inducing (cytotoxic) as opposed to a suppressive (cytostatic) treatment option for patients with LAM, combined with strong pre-clinical evidence demonstrating the efficacy of a combination of sirolimus and resveratrol form the basis for this dose-escalating, safety and efficacy clinical trial. Results from this trial will pave the way for pivotal phase III, randomized, controlled, efficacy studies of combined resveratrol and sirolimus in LAM.

Clinical Phase	II
IND Sponsor	[name], University of Cincinnati, Cincinnati OH
IND Number	131722
Principal Investigator	[name], University of Cincinnati, Cincinnati OH
Participating Site(s)	University of Cincinnati - Cincinnati, OH
Accrual Objective	20 evaluable subjects 25 target enrollment
Study Objectives	Phase II dose-escalating, open-label, safety and efficacy study to determine if there is a potential benefit of resveratrol in combination with sirolimus in patients with LAM. Based on the results of this trial, additional phase III clinical development trials may be designed.
Study Design	Phase II: Open label, intention to treat study
Study Duration	24 weeks treatment
Primary Objective	Assess the change in serum VEGF-D level after 24 weeks of treatment with a combination of resveratrol and sirolimus as compared to the VEGF-D level in patients on a stable dose of sirolimus alone.
Secondary Objectives	
 
1. Assess the safety and adverse effect profile of combined resveratrol and sirolimus in adult patients with LAM.
 

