#### **6.5 Patient retention and drug compliance**

Patient retention will be encouraged in several ways. Extensive contact information will be captured for each patient, at the time of study enrollment. This will include home, work, and cellular telephone numbers and that of an emergency contact or nearest family member. Prior to each study visit, the study staff will contact the patient to remind her about the upcoming study visit. A check for the reimbursement of expenses up to \$500 will be issued after each study visit.

The study staff and physician will explain the importance of compliance with the study protocol at each patient contact. If a patient fails to comply with a study visit, the study staff will contact her by telephone. If the study staff is unsuccessful in reaching the patient, a follow up letter will be sent by overnight carrier, on two consecutive weeks, seeking follow-up.

Compliance with the protocol and drug administration will be strongly emphasized. Pill counts will be performed at visits and episodes of medication noncompliance will be recorded, including the reason for noncompliance. Patients will receive a calendar to document medication and any side effects experienced that day. If a patient wishes to withdrawal from the treatment phase of the study or has a serious adverse event (SAE) (whether related to study drugs or not), patient follow-up assessments will continue for safety monitoring and to avoid problems associated with missing data. The inclusion of such follow-up data will allow for analysis by intention-to-treat.

If a patient is withdrawn from study drug exposure for any reason, the patient will be strongly encouraged to continue with and complete the remainder of the study assessments, as scheduled.

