#### **12.3.5 Prohibited medications**

Participants will not be allowed to receive any concomitant medication(s) that may interfere in the interpretation of data or the subject's participation in the study in the Investigator's opinion.

Metabolism of sirolimus occurs in the liver and the small intestine by the CYP3A4 family of enzymes. Thus, concomitant administration of sirolimus with other CYP3A substrates or inducers can alter the oral bioavailability of sirolimus (59). Although not a strong modulator of CYP activity, resveratrol has been reported to inhibit the activity of CYP3A4 *in vitro* and *in vivo* (60). Thus, co-administration of sirolimus and resveratrol has the potential to increase the blood levels of sirolimus or lead to an increase in the side effects of sirolimus. We will periodically monitor the sirolimus level during the study, as well as monitor closely for any adverse effects related to the study medications.

Because of the potential interaction with other drugs involving CYP3A4 metabolic pathways, strong inhibitors and strong inducers of CYP3A4 will not be allowed to be used concomitantly with the study medication. A washout period of 14 days will be required after discontinuation of the below listed medications before beginning the study medication. A list of the prohibited medications is provided in Table 4 below:

List of prohibited medications for this study
Strong CYP inducers
Barbiturates
Carbamazepine
Phenytoin
Rifampin, Rifabutin
St. John's Wort
Strong CYP inhibitors
Ketoconazole
Voriconazole
Itraconazole
Nefazodone
Clarithromycin
Erythromycin
Telithromycin
Gemfibrozil
Grapefruit juice

**Table 4:** List of prohibited medications for this study

Concomitant use of resveratrol with drugs with a narrow therapeutic range that are CYP3A, CYP1A2, CYP2D6, or CYP2C9 substrates (for example, theophylline,

tizanidine, warfarin, phenytoin, alfentanil, dihydroergotamine, ergotamine, fentanyl, pimozide, quinidine, cyclosporine, tacrolimus, thioridazine) will be prohibited from Day 1 until the end of study.

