## **14.4 Collecting, recording and managing adverse events**

### **14.4.1 Identifying adverse events**

Any adverse event that occurs from the moment the subject has signed the consent form will be recorded and is reportable. Collection time for AEs and SAEs will begin after the screening visit when the consent form is signed and will continue until the end of the treatment.

Adverse events may be discovered through any of these methods:

- Observing the participant
- Questioning the participant, with standardized questions/procedures.
- Receiving an unsolicited complaint from the participant.
- An abnormal value or result from a clinical or laboratory evaluation can also indicate an adverse event when determined to be clinically significant by the Principal Investigator.

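### Visit 3 dispenses 12 weeks of resveratrol when 8 weeks of treatment remain, and Visit 4 has no step to retrieve the surplus

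*Combined protocol and SAP*

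**What the plan says.** The dispensing instructions are in the visit lists of Section 6.3.

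- Screening/Initial Visit: "Dispense resveratrol tablets for the next 8 week supply".
- Visit 2 (week 8): "Dispense resveratrol tablets for the next 8 weeks".
- Visit 3 (week 16): "Dispense resveratrol tablets for the next 12 weeks".
- Visit 4 (week 24): nothing is dispensed. The list includes a review of the drug diary but no collection of unused drug.

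The Synopsis gives the study duration as "24 weeks treatment". Section 5.6 has patients who tolerate escalation stay on the week 16 dose for the remainder of the study and describes no dosing after that. Visit 4 leaves later treatment to the patient and her regular physician.

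On adherence, Section 6.5 says: "Pill counts will be performed at visits and episodes of medication noncompliance will be recorded, including the reason for noncompliance". Section 11.4 also relies on pill counts. Neither gives a formula.

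**The concern.** Visits 1 and 2 each hand out exactly what is needed to reach the next visit. Visit 3 does not, and nothing in the protocol explains the difference. Because this is an instruction that staff will follow, the extra drug would reach every patient who attends Visit 3.

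It matters because Section 12.3.5 warns that "co-administration of sirolimus and resveratrol has the potential to increase the blood levels of sirolimus". For that reason Section 12.3.3 schedules trough levels at weeks 2, 4, 8, 12, 16, 18, 20 and 24, and none later. After Visit 4 the only planned contact is the telephone call at week 28 ± 7 days, which is limited to adverse events still open. Twelve weeks counted from week 16 also ends at week 28. A coordinator could therefore take the Visit 3 line as permission to dose up to that call, although no section describes dosing in that interval.

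**Working it through.** **Inputs**

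| Quantity | Value | Source |
|---|---|---|
| Treatment period | 24 weeks | Synopsis, Study Duration |
| Supply at Visits 1, 2, 3 | 8, 8, 12 weeks | Section 6.3 |
| Visits 1, 2, 3, 4 | weeks 0, 8, 16, 24 | Sections 6.2 and 6.3 |
| Window after the initial visit | ±7 days | Section 6.2 |
| Dose levels | 250, 500, 1000 mg daily | Section 5.6; Table 3 |
| Capsule strength | 125 mg | Section 11.1 |

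**1. Supply needed at each visit** = week of next visit − week of current visit.

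- Visit 1: 8 − 0 = 8 weeks; 8 dispensed. Reproduced.
- Visit 2: 16 − 8 = 8 weeks; 8 dispensed. Reproduced.
- Visit 3: 24 − 16 = 8 weeks; 12 dispensed. Not reproduced.

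Total: 8 + 8 + 12 = 28 weeks supplied, and 28 − 24 = 4 weeks over.

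**2. Can the visit windows explain 12 weeks?**

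- Longest Visit 3 to Visit 4 interval: 25 − 15 = 10 weeks, leaving 12 − 10 = 2 weeks.
- Shortest interval: 23 − 17 = 6 weeks, leaving 12 − 6 = 6 weeks.

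Some drug is left over in every case within the windows. The range is 2 to 6 weeks.

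**3. The nominal surplus in capsules** = (daily dose / 125) × 28 days.

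| Daily dose | Capsules per day | Due in 56 days | Supplied for 84 days | Surplus |
|---|---|---|---|---|
| 1000 mg | 8 | 448 | 672 | 224 |
| 500 mg | 4 | 224 | 336 | 112 |
| 250 mg | 2 | 112 | 168 | 56 |

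This assumes that the quantity dispensed follows the patient's own dose. (Section 6.3 speaks of tablets and Section 11.1 of capsules; the counts use the latter.)

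**4. Pill-count adherence.** The protocol gives no denominator, so the following is illustrative only. Take a patient on 1000 mg daily who takes every dose for 56 days.

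- Capsules taken over capsules due: 448/448 = 100%.
- Capsules taken over capsules dispensed: 448/672 = 66.7%.
- Unreturned capsules counted as taken, over capsules due: 672/448 = 150%.

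**5. Primary endpoint.** A patient who doses as scheduled reaches the surplus only after Visit 4, when the week 24 VEGF-D sample has been drawn. The paired comparison in Section 15 and its sample size do not involve it.

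**The case against.** The best defence is that spare drug in hand is not dosing. No section describes resveratrol after week 24, and Visit 4 returns treatment decisions to the patient and her physician. This is correct. The documents show only that surplus drug would be available and that the wording is open to misreading, not that patients would take it.

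The extra could also be an allowance for late visits. The windows account for at most 10 weeks, and Visits 1 and 2 carry no allowance, so this does not explain the figure.

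Section 7.2 allows up to 28 weeks of participation, which might suggest treatment to week 28. But that figure expressly counts the follow-up call, and Section 5.7 refers to a 24-week study duration.

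Finally, counting is already required. Section 6.5 applies to all visits, Visit 4 included, and the lists for Visits 2 and 3 omit a pill count too, so its absence at Visit 4 is not a special gap. Section 11.3 also requires accounting for each participant. This objection stands. What is missing is narrower: a step to get the unused capsules back. Section 13.2 foresees retrieving drug from patients lost to follow-up, but the Visit 4 list has no equivalent for those who complete.

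**Conclusion.** The Visit 3 supply contradicts the 24-week treatment period, the final visit at week 24 and the pattern at the first two visits. The surplus is nominally 4 weeks, and 2 to 6 weeks within the visit windows, assuming that doses are taken as scheduled. The figure of 224 capsules applies only to patients on 1000 mg daily. This is a minor inconsistency affecting drug accountability and safety follow-up. It does not touch the primary analysis, sample size or error rate.

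Three stronger readings are tempting, and the documents do not support them.

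- *Adherence is distorted.* A reader might infer that a fully adherent patient would score 67%. That needs a formula the protocol does not contain, and the effect disappears if capsules taken are set against capsules due. Section 15 plans no adherence analysis. A distortion is possible but not shown.
- *The surplus could trigger withdrawal for continued non-compliance (Section 13.1.4).* The final-period count can be completed only at Visit 4, when treatment is over.
- *Patients would be dosing after adverse-event collection has closed.* Section 14.4.1 says collection "will continue until the end of the treatment", which is tied to treatment and not to Visit 4. Whether it would have closed while a patient was still taking leftover drug is unclear.

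**What to change.** 1. Reconcile the Visit 3 quantity in Section 6.3 with the Synopsis (Study Duration), Section 5.6 and Visit 4. The sponsor decides which is intended; this review takes no position on the supply or the treatment period.
2. Add a line to the Visit 4 list for retrieving unused capsules, so that the pill count required by Section 6.5 can be completed for the final period.

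It would also help, though the point does not depend on it, to state the adherence denominator in Section 11.4.

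The cost is a wording change at Visits 3 and 4. No added visit, assay or patient is needed, and the statistical analysis does not change.
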